8.2 Adverse Events

8.2.1 Definition of Adverse Events and Serious Adverse Events

An AE is defined as any untoward medical occurrence in a patient or clinical investigation subject administered a pharmaceutical product, which does not necessarily have to have a causal relationship with this treatment.

Test results collected during the study (e.g., laboratory values, physical examination, ECGs, etc.) or identified from review of other documents may constitute AEs if deemed clinically significant.

A SAE is defined as any AE that:

- results in death.
- is life threatening.
- requires inpatient hospitalization or prolongation of existing hospitalization (hospitalization for elective procedures or for protocol compliance is not considered an SAE).
- results in persistent or significant disability/incapacity.
- is a congenital anomaly/birth defect.
- important medical events that do not meet the preceding criteria but based on appropriate medical judgement may jeopardize the patient or may require medical or surgical intervention to prevent any of the outcomes listed above.

8.2.2 Eliciting and Reporting Adverse Events/Serious Adverse Events

Patients will be instructed to contact the Investigator at any time after ICF signature if any symptoms develop. At each study visit, patients will be asked a non-leading question to elicit any medically related changes in their well-being. Patients may also report AEs voluntarily and they will be instructed to contact the Investigator between visits if any symptoms develop or worsen.

AEs will be reported starting when the patient provides written informed consent. Clinically significant medical conditions present at the time of ICF signature will be reported as medical history. Clinically significant medical conditions that start or worsen after ICF signature will be reported as AEs.

All AE/SAEs, regardless of relationship to study drug, will be reported from the time the patient signs the ICF until 30 days after the last dose of study drug or start of new anti-cancer therapy, whichever is earlier; thereafter, only related SAEs will be reported, with 2 exceptions.

1. Patients who have responded to loncastuximab tesirine and undergo SCT (either autologous or allogeneic) after permanent discontinuation of loncastuximab tesirine treatment without any intervening anti-cancer therapy. These patients will have the following safety information reported until 180 days post-transplant regardless of relationship to loncastuximab tesirine:
 - Grade ≥ 3 AEs suggestive of hepatic toxicity, veno-occlusive disease/sinusoidal obstruction syndrome, graft-versus-host disease, infectious complications, prolonged cytopenia(s), and pulmonary toxicity
 - SAEs
 - Death

2. Patients who receive CAR-T therapy after permanent discontinuation of loncastuximab tesirine treatment will have the following safety information reported until 90 days after receiving CAR-T therapy regardless of relationship to loncastuximab tesirine:
 - Grade ≥ 3 AEs of cytokine release syndrome, encephalopathy, edema or effusion, rash, hepatic toxicity
 - SAEs
 - Death

Whenever possible, AEs should be reported as a diagnosis rather than individual signs and symptoms. If no diagnosis is available or has been identified, then the primary symptom is reported.

In general, the term ‘disease progression’ should not be used for reporting an AE/SAE. However, AEs/SAEs that are complications of disease progression should be reported.

All AEs reported or observed during the study will be recorded on the AE page of the eCRF. Information to be collected will include event term, date of onset, assessment of severity ([Section 8.2.3](#)), seriousness ([Section 8.2.1](#)), relationship to study drug ([Section 8.2.4](#)), action taken with study drug, date of resolution of the event or ongoing (when no resolution by the end of the reporting period), any required treatment or evaluations, and outcome.

New SAEs and any recurrent episodes, progression, or complications of the original SAE must be reported to the pharmacovigilance department of the Sponsor or delegate (e.g., contract research organization [CRO]) within 24 hours after the time site personnel first learn about the event. Reporting will occur through the electronic data capture (EDC) system.

8.2.3 Assessment of Severity

AEs will be graded according to CTCAE v4.0. For events not included in the CTCAE criteria, the severity of the AE is graded on a scale of 1 to 5 as shown in [Table 3](#).

Table 3. Definition of Severity Grades for CTCAE

Grade	Definition
1	Mild; asymptomatic or mild symptoms; clinical or diagnostic observations only; intervention not indicated.
2	Moderate; minimal, local or noninvasive intervention indicated; limiting age-appropriate instrumental activities of daily living (ADL). ^a
3	Severe or medically significant but not immediately life threatening; hospitalization or prolongation of hospitalization indicated; disabling; limiting self-care ADL. ^b
4	Life-threatening consequences; urgent intervention indicated.
5	Death related to adverse event.

^a ADL refers to preparing meals, shopping for groceries or clothes, using the telephone, managing money, etc.

^b Self-care ADL refers to bathing, dressing and undressing, feeding self, using the toilet, taking medications, and not bedridden.

AEs characterized as intermittent do not require documentation of onset and duration of each episode.

8.2.4 Assessment of Causality

The Investigator's assessment of an AE's relationship to study drug is an important part of safety reporting, but is not a factor in determining whether an AE is reported. An AE will be assessed as related to study drug if there is a reasonable possibility of causal relationship with the use of the study drug. For SAEs, whenever possible, the Investigator should provide a rationale for the causality assessment.

8.2.5 Regulatory Reporting

All SAEs considered at least possibly related to the study drug will be reported as Suspected Unexpected Serious Adverse Reactions (SUSARs), unless they have been defined as expected in the Reference Safety Information section of the IB. SUSARs will be reported to competent authorities and independent ethics committee (IEC) in accordance with current legislation.

8.2.6 Pregnancy

Any pregnancy in a participant or partner that occurs during the study must be reported using the Pregnancy Report Form. Pregnancy must be reported within 24 hours after the site personnel first learn of the pregnancy. The pregnancy itself is not considered an AE. However, the pregnancy must be followed to determine outcome (including spontaneous miscarriage, elective termination, normal birth, or congenital abnormality) and status of mother and child, even if the patient discontinued from the study. Abortions (elective or spontaneous) occurring from the time the patient signs the ICF until 90 days after the last dose of study drug must be reported as an SAE.

Any SAE occurring in association with a pregnancy that is brought to the Investigator's attention after the patient has completed the study and considered by the Investigator as possibly related to the study drug must be promptly reported in the same manner.

Once pregnancy is confirmed in a study participant, study drug will be discontinued, see [Section 8.3.6](#) for additional information.

8.2.7 Overdose

An overdose of the study drug will be considered an AE if the dose administered to the patient exceeds the maximum dose described in the protocol by 15% or more. If such an overdose occurs during the study, with or without any signs or symptoms, it must be reported to the Sponsor using the SAE Report Form within 24 hours after the time site personnel first learn about the event.

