2.2 Rationale for Dose Selection

For patients with relapsed or refractory non-Hodgkin lymphoma, available data support a loncastuximab tesirine dosing regimen of 150 $\mu\text{g}/\text{kg}$ every 3 weeks (Q3W) \times 2 cycles, followed by a 50% reduction to 75 $\mu\text{g}/\text{kg}$ Q3W for the Phase 2 trial. For safety, particular differences in predicted probabilities (pp) were apparent between the 200 $\mu\text{g}/\text{kg}$ Q3W and 150 $\mu\text{g}/\text{kg}$ Q3W doses, respectively, including Grade ≥ 3 edema (pp=0.2817 vs. 0.1070 in patients with prior stem cell transplant), liver function test-related toxicities (pp=0.4018 vs. 0.1644 in patients with prior relapsed disease; 0.4018 vs. 0.1644 in patients without prior stem cell transplant; pp=0.5208 vs. 0.2203 in patients with body mass index [BMI] of 35 kg/m^2 , and pp=0.4018 vs. 0.1644 in patients with baseline Eastern Cooperative Oncology Group [ECOG] of 0 or 1, respectively), and neutropenia or neutrophil decrease (pp=0.4383 vs. 0.2865).

For efficacy, the decision for initial dosing at the 150 µg/kg dose level is predicated on higher observed and predicted ORR as compared to the 120 µg/kg and lower doses. The decision to dose reduce following 2 cycles of treatment was based on the rapid onset of response observed in a majority of patients (median 2 cycles), and desire to mitigate onset of late-developing and difficult to manage toxicities, such as edema. Initial dosing for 2 cycles is anticipated to optimize the frequency of objective response, while dose reduction in subsequent cycles will permit continued exposure with manageable toxicity to optimize the durability of response.

3 Study Objectives and Endpoints

Table 2. Study Objectives and Endpoints

Objectives	Endpoints
Primary	
Evaluate the efficacy of single agent loncastuximab tesirine in patients with relapsed or refractory DLBCL	ORR according to the 2014 Lugano classification (Cheson et al. 2014) as determined by central review in all treated patients; ORR is defined as the proportion of patients with a best overall response (BOR) of CR or PR
Secondary	

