6.3 Loncastuximab Tesirine Dosing

Administration of loncastuximab tesirine will be performed by the Investigator or a qualified designee.

Loncastuximab tesirine will be administered as an IV infusion over 30 minutes on Day 1 of each cycle (every 3 weeks) at a dose of 150 µg/kg Q3W for 2 cycles, then 75 µg/kg Q3W. Refer to [Section 6.6](#) for premedication and supportive care.

Patients with a BMI ≥ 35 kg/m² will have their dose calculated based on an adjusted body weight as follows:

$$\text{Adjusted body weight (ABW) in kg} = 35 \text{ kg/m}^2 * (\text{height in meters})^2$$

$$\text{Dose to administer (mg)} = \text{dosage (}\mu\text{g/kg)} * \text{ABW} / 1000$$

Extravasation of loncastuximab tesirine may be associated with local irritation, swelling, pain, or tissue damage. The IV infusion site should be monitored for signs of IV infiltration or drug extravasation, and patients should be instructed to report immediately any signs of IV infiltration or drug extravasation during or after the infusion. Suspected extravasation of loncastuximab tesirine should be managed according to institutional protocol for management of extravasation of cytotoxic chemotherapy. For patients who have a central line, administration of loncastuximab tesirine via this central line should be considered.

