6.4 Dose Delays and Modifications

If a patient experiences any Grade ≥ 3 (≥ 2 for edema, effusion, or increased AST/ALT/GGT) non-hematologic toxicity, loncastuximab tesirine must be held until the toxicity resolves to Grade ≤ 1 (Grade 1 or baseline for peripheral neuropathy). In addition, if a patient experiences hematological toxicity of Grade ≥ 3 neutropenia or thrombocytopenia, loncastuximab tesirine must be held until the toxicity resolves to Grade ≤ 2 .

If loncastuximab tesirine dosing is delayed by more than 3 weeks and the toxicity is considered at least possibly related to loncastuximab tesirine, then subsequent doses of loncastuximab tesirine will be reduced by 50%. In addition, the Investigator may reduce the dose of loncastuximab tesirine by 50% for any Grade ≥ 3 (≥ 2 for edema, effusion, or increased

AST/ALT/GGT) toxicity that is possibly related to loncastuximab tesirine, but does not result in dosing delay of more than 3 weeks if they feel it is in the best interest of the patients.

If toxicity requiring dose reduction as described above occurs following the second dose of 150 µg/kg (C2D1), the patient should receive the per protocol-defined dose of 75 µg/kg for Cycle 3.

If toxicity as described above recurs at the reduced dose, subsequent doses of loncastuximab tesirine will be reduced by an additional 50%.

If toxicity as described above recurs after a second dose reduction, study drug must be discontinued permanently.

If loncastuximab tesirine dosing is delayed by more than 5 weeks and the toxicity is considered at least possibly related to loncastuximab tesirine, study drug must be discontinued permanently unless continued administration is approved by the Sponsor.

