6.5 Overdose Management

An overdose is any dose of study drug given to a patient that exceeds the dose described in the protocol. There are no data available to determine what the effects of overdose are and whether they can be reversed. Symptomatic treatment and standard supportive care measures for the management of any observed toxicity should be applied.

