4.3 Protocol Deviations

The number and percentage of patients with any important clinical study report (CSR) reportable protocol deviation will be summarized overall and by type of deviation. The pre-defined important CSR reportable protocol deviations are listed below; in addition, any other protocol deviations deemed by ADCT medical to be important CSR reportable deviations will be included in the summary.

1. Patient entered the study even though they did not satisfy the entry criteria
2. Patient received a prohibited concomitant treatment during the study
3. Patient who met criteria for mandatory withdrawal of study drug during the study but did not have study drug withdrawn
4. Patient who received the wrong treatment or incorrect dose, specifically:
 - Actual dose of study drug was greater than 15% more or less than protocol defined planned dose level.
 - Patient started next cycle less than 18 days after Day 1 of the most recent treatment cycle.

Important protocol deviations will be listed.

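### Protocol 8.2.7 measures overdose against the wrong dose: from Cycle 3 a mistaken 150 µg/kg, twice the planned dose, does not trigger the 24-hour report

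*Protocol*

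**What the plan says.** Protocol 6.3 gives the regimen "at a dose of 150 µg/kg Q3W for 2 cycles, then 75 µg/kg Q3W". Section 2.2 describes the step-down as "followed by a 50% reduction to 75" µg/kg and gives as one reason the "desire to mitigate onset of late-developing and difficult to manage toxicities, such as edema". Section 6.4 allows lower doses still: after a delay of more than three weeks for drug-related toxicity, "then subsequent doses of loncastuximab tesirine will be reduced by 50" per cent, and a recurrence leads to a further halving.

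Two sections of the protocol deal with overdose. Section 6.5 defines it generally, as any dose above the one the protocol describes. It sets no margin and no reporting duty, and it adds: "There are no data available to determine what the effects of overdose are and whether they can be reversed". Section 8.2.7 sets the duty. An overdose counts as an AE if it "exceeds the maximum dose described in the protocol by 15% or more", and in that case, "with or without any signs or symptoms, it must be reported to the Sponsor using the SAE Report Form within 24 hours" of the site learning of it.

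The SAP uses a different reference. Section 4.3 lists as an important deviation: "Actual dose of study drug was greater than 15% more or less than protocol defined planned dose level".

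**The concern.** The regimen has one planned dose change, the halving at Cycle 3. Failing to make it is a foreseeable error (a judgement; the documents give no error rate), and it produces exactly 150 µg/kg. Because 8.2.7 refers to the protocol's maximum and not to the dose planned for that patient and cycle, this error falls below its trigger.

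What is at stake is prompt safety notice. The step-down is there to limit toxicity that appears late, so an overdosed patient may have no symptoms at first. Section 8.2.7 is written for that situation, since it applies whether or not there are symptoms. An asymptomatic overdose below its trigger is also not an AE under that section, so the section would not bring it into the TEAE summaries.

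**Working it through.** **Inputs**
- Planned dose: 150 µg/kg in Cycles 1–2, then 75 µg/kg (Protocol 6.3).
- Step-down: 50% (Protocol 2.2).
- Margin: 15% or more above the protocol maximum (Protocol 8.2.7).
- Toxicity reductions: 50% each, at most two before permanent discontinuation (Protocol 6.4).

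**The plan's own figure.** 150 × 0.5 = 75 µg/kg, which agrees with 2.2 and 6.3.

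**Trigger as written.** 1.15 × highest protocol dose = 1.15 × 150 = 172.5 µg/kg, the same in every cycle.

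**Trigger against the planned dose.** 1.15 × dose planned for that patient and cycle.

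| Planned dose (µg/kg) | Trigger as written (µg/kg) | That trigger ÷ plan | Mistaken 150 ÷ plan | Trigger against plan (µg/kg) |
|---|---|---|---|---|
| 150 | 172.5 | 1.15 | 1.0 | 172.5 |
| 75 | 172.5 | 2.3 | 2.0 | 86.25 |
| 37.5 | 172.5 | 4.6 | 4.0 | 43.125 |
| 18.75 | 172.5 | 9.2 | 8.0 | 21.5625 |

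The last two rows assume one and two 50% reductions made from 75 µg/kg: 75 × 0.5 = 37.5 and 37.5 × 0.5 = 18.75. They do not describe a patient whose toxicity follows the second 150 µg/kg dose, because 6.4 gives that patient the usual 75 µg/kg at Cycle 3. The 75 µg/kg row also applies to a patient halved at Cycle 2 after toxicity in Cycle 1.

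**Result.** At a planned 75 µg/kg, a mistaken 150 µg/kg is 150/75 − 1 = 100% above plan but 150/150 − 1 = 0% above the protocol maximum. The rule as written does not apply; a rule based on the planned dose would.

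**Other routes to the Sponsor**
- Protocol 6.2.3: the site records departures from the dispensing regimen, with no deadline.
- Protocol 8.2.2: AEs are reported, and SAEs within 24 hours. This needs an event, not just a wrong dose.
- SAP 4.3 and 4.7.1: the error appears in the deviation summary and the exposure listing. These are analysis outputs and give no prompt notice.

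None of these sets a 24-hour report for an overdose without symptoms.

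**The case against.** The strongest reply is that the maximum in 8.2.7 was meant per cycle. Section 6.5 defines overdose against the described dose, which changes by cycle, and SAP 4.3 applies the same 15% to the planned level. A site that recognises an overdose under 6.5 might read 8.2.7 the same way. That is a possible reading, but the text does not support it: 8.2.7 adds the word *maximum*, which 6.5 does not use, and mentions neither cycle nor patient. A 24-hour duty should not depend on how each site resolves this.

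A second reply is that the high threshold was deliberate, keeping expedited reports for doses no patient should ever receive. Every patient starts at 150 µg/kg, and 2.2 gives model-predicted toxicity for 150 µg/kg every three weeks, so the absence of overdose data noted in 6.5 should not be pressed too far for that dose. This much stands. But no such purpose is stated, and it would fit poorly with a step-down meant to limit late toxicity.

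Third, the gap is narrow. The error is not lost, and what is missing is the speed of notice and the AE status of a wrong dose without an SAE. This also stands, and the documents do not show how often it would happen. An investigator could report a doubled dose as an important medical event under 8.2.1, but that is discretionary. The pharmacy manual and eCRF guidelines were not available and might say more.

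**Conclusion.** The concern holds. Followed as written, 8.2.7 has a trigger of 172.5 µg/kg in all cycles. From Cycle 3 it therefore misses a repeated 150 µg/kg (2.0 times plan) and anything up to just under 2.3 times plan; after one further reduction to 37.5 µg/kg the trigger is 4.6 times plan.

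This rests on the plain meaning of the protocol's maximum dose and on the protocol and SAP alone. Confidence is medium, because a per-cycle meaning may have been intended although it is not stated. It is a safety-reporting fault that should be corrected. It has no bearing on the response-rate analysis, type I error, power or sample size.

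**What to change.** In Protocol 8.2.7, replace the reference to the protocol's maximum dose with *the patient's planned dose for that cycle, after any dose reduction*. Keep the 15% margin and the 24-hour report. Section 6.5 can stay as the general definition, and SAP 4.3 needs no change because it already refers to the planned dose level.

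The trigger is then unchanged in unreduced Cycles 1–2 and follows the planned dose afterwards. The cost is one phrase at the next amendment and possibly a few more overdose reports.

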8.3 Safety Assessments

Safety will be assessed based on the procedures in the subsection below. AEs/SAEs collection and reporting is described in [Section 8.2.2](#).

Unless otherwise specified, all safety assessments on dosing days will be done prior to study drug administration.

8.3.1 Physical Examination

Physical examination will be performed according to institutional standards and will include a whole body skin examination.

8.3.2 ECOG Performance Status

ECOG performance status grades are presented in [Appendix 1](#) and will be captured as per SoE ([Table 1](#)).

8.3.3 Height and Weight

Height and weight will be measured as per SoE ([Table 1](#)).

Additional measurements will be performed if clinically indicated.

Patients should monitor their weight at home to mitigate the risks for edema/effusions. Refer to [Section 6.6.2](#) for further details.

8.3.4 Vital Signs

Vital signs include the measurements of arterial blood pressure (systolic and diastolic), heart rate, respiratory rate, and body temperature and will be performed according to the institutional standards. For Day 1 of each cycle, vital signs are to be measured before the start of the loncastuximab tesirine infusion and at the end of infusion.

8.3.5 Laboratory Tests

Samples will be collected at the time points specified as per SoE ([Table 1](#)).

Any clinically significant abnormal laboratory test results will be recorded as AEs or SAEs.

Hematology: white blood cells (WBC) with 5-part differential (neutrophils, eosinophils, basophils, lymphocytes, and monocytes), platelet count, hemoglobin, and hematocrit.

Chemistry: ALT, AST, GGT, alkaline phosphatase (ALP), amylase, lipase, total bilirubin (conjugated and unconjugated bilirubin only when total bilirubin is abnormal), sodium, potassium, chloride, phosphate, calcium, magnesium, blood urea nitrogen or urea, carbon dioxide/bicarbonate, creatinine, creatine phosphokinase, total protein, albumin, glucose, and lactate dehydrogenase.

Coagulation: partial thromboplastin time (PTT) and International Normalized Ratio (INR).

Urinalysis: pH, specific gravity, protein, WBC, red blood cell (RBC), ketones, glucose, and bilirubin.

Urinalysis may be performed by dipstick. Abnormal findings will be followed up with a microscopic evaluation and/or additional assessments as clinically indicated. A microscopic evaluation consists at a minimum of WBC and RBC quantitation per high power field, as well as semi-quantitative assessment of other cells and substances, if present, such as epithelial cells, bacteria, and crystals (“few,” “moderate,” “many”). Other evaluations depending on microscopic findings may be added.

8.3.6 Pregnancy Test

A highly sensitive β -HCG test in urine or blood β -HCG test will be performed in woman of childbearing potential for eligibility (see [Section 5.1](#) Inclusion criterion 10) and throughout the study as per SoE.

The C1D1 pre-dose pregnancy test can be waived if the test for eligibility was done within 3 days of C1D1. After starting the study drug, all efforts should be made to keep the interval between 2 consecutive pregnancy tests no more than 6 weeks.

If a pregnancy test is positive, the study drug must be held pending confirmation. If the pregnancy is confirmed, treatment will be discontinued permanently for the patient. Refer to [Section 8.2.6](#) for the handling of the patient and reporting the event.

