Medical/Cancer history	9.5	X						
██████████	██████████	██████████						
Physical examination	8.3.1	X	X			X	X	
ECOG performance status	8.3.2	X	X			X	X	
Height	8.3.3	X						
Weight	8.3.3	X	X	X	X	X	X	
Vital signs (BP, HR, RR, Temp)	8.3.4	X	X	X	X	X	X	
Disease assessment ²	8.1	X	6 weeks and 12 weeks after C1D1, then every 9 weeks				X ²	Every 12 weeks until 1 year from EOT, then every 6 months until disease progression ³
Hematology and Chemistry	8.3.5	X	X ⁴	X	X	X ⁴	X	
Coagulation and Urinalysis	8.3.5	X						
Pregnancy test, if applicable	8.3.6	X	X ⁵			X	X	
12-lead ECG	8.3.7 Table 4	X	X (pre-infusion, EOI, and 4 h post-infusion)	X	X	Every other cycle (C3, pre-infusion and EOI; C5 and beyond, pre-infusion only)	X	
Premedication	6.6.1		D-1 to D2			D-1 to D2		
Loncastuximab tesirine administration	6.3		X			X		

	Protocol Section	Screening	Treatment Period				EOT	Follow-up Period (up to 3 years from EOT) Every 12 weeks
			Cycle 1 and Cycle 2 (C1 and C2)		C3 and beyond			
(1 Cycle = 3 weeks)			1	8	15	1		
Day (D)		-28 to -1	1	8	15	1		
PK sample	8.4.1 Table 5		X (pre-infusion, EOI, and 4 h post-infusion)	X	X	Every other cycle (C3, pre-infusion and EOI; C5 and beyond, pre-infusion only)	X	
ADA sample	8.4.2 Table 5		X (pre-infusion)		X ⁶	Every other cycle (C3 and beyond, pre-infusion only)	X ⁷	
gDNA and cfDNA samples	8.4.3		X				X	
HRQoL	8.5		X			X	X	
Concomitant medications	6.7	From ICF signature date or D-14 whichever is earlier, until at least 30 days after last dose of study drug						
Adverse events	8.2	CTCAE, Version 4.0 AE/SAEs from ICF signature date until at least 30 days after last dose of study drug; thereafter related SAEs only						
1 st New anticancer treatment							X	
Survival							X	

Abbreviations: ADA, anti-drug antibody; AE, adverse event; BP, blood pressure; cfDNA, circulating cell-free DNA; CTCAE, Common Terminology Criteria for Adverse Events; ECG, electrocardiogram; ECOG, Eastern Cooperative Oncology Group; EOI, end of infusion; EOT, end of treatment; gDNA, genomic DNA; HR, heart rate; HRQoL, health-related quality of life; ICF, informed consent form; PET-CT, Positron emission tomography - computed tomography; PK, pharmacokinetics; RR, respiratory rate; SAE, serious adverse event; Temp, temperature.

¹ Tumor tissue should be submitted once all other eligibility criteria have been met.

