² Screening imaging (PET-CT) must be performed within 4 weeks prior to C1D1 and the same assessment method should be used throughout the study. Week 6 imaging should be performed within 5 days prior to C3D1 and Week 12 imaging should be performed within 5 days prior to C5D1. All other imaging for disease assessment for patients on study drug should be performed within ± 2 weeks of the scheduled timepoint. Disease assessments should be performed at the timepoints specified even if study drug dosing is delayed. If a scan has been performed within 8 weeks of EOT, it does not need to be repeated at EOT.

³ Disease assessments to be performed in patients having discontinued study drug for reasons other than disease progression.

⁴ ≤3 days prior to administration of study treatment, unless more frequent testing is clinically indicated.

⁵ Not needed if screening assessment was performed within 7 days prior to C1D1.

⁶ Cycle 1 only

⁷ Patients who test positive for ADAs will be requested to supply additional ADA samples as per [Section 8.4.2](#).

Visit Scheduling Windows:

- Treatment Period: visit day ± 2 days (excluding C1D1 which is the reference day)
- EOT: as soon as possible after decision to discontinue the study drug, preferably within 30 days after last dose of study drug, and before initiation of any new anticancer treatment
- Follow-up Period: visit day ± 14 days

1 Introduction and Background

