4.2 Screening Period

Informed consent must be obtained for each patient and documented with a signed informed consent form (ICF) prior to any study procedures. Procedures that are performed as part of standard of care (SOC) may be used to satisfy screening requirements if they are performed in the appropriate window.

The screening period is from 28 days to 1 day prior to the start of the study drug. The screening assessments should be performed within this period in order to assess the eligibility of the patient against the inclusion and exclusion criteria ([Sections 5.1](#) and [5.2](#), respectively).

See [Section 5.3](#) for the information to be collected on screening failures.

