5.1 Inclusion Criteria

1. Male or female patient aged 18 years or older.
2. Pathologic diagnosis of DLBCL, as defined by the 2016 WHO classification, to include: DLBCL not otherwise specified; primary mediastinal large B-cell lymphoma; and high-grade B-cell lymphoma, with *MYC* and *BCL2* and/or *BCL6* rearrangements
3. Relapsed or refractory disease following two or more multi-agent systemic treatment regimens
4. Patients who have received previous CD19-directed therapy must have a biopsy that shows CD19 protein expression after completion of the CD19-directed therapy.
5. Measurable disease as defined by the 2014 Lugano Classification ([Appendix 2](#)).
6. Availability of formalin-fixed paraffin-embedded (FFPE) tumor tissue block (or minimum 10 freshly cut unstained slides if block is not available).

Note: Any biopsy since initial diagnosis is acceptable, but if several samples are available, the most recent sample is preferred.

7. ECOG performance status 0-2.
8. Adequate organ function as defined by screening laboratory values within the following parameters:
 - a. Absolute neutrophil count (ANC) $\geq 1.0 \times 10^3/\mu\text{L}$ (off growth factors at least 72 hours).
 - b. Platelet count $\geq 75 \times 10^3/\mu\text{L}$ without transfusion in the prior 7 days.
 - c. Alanine aminotransferase (ALT), aspartate aminotransferase (AST), and gamma glutamyl transferase (GGT) $\leq 2.5 \times$ the upper limit of normal (ULN).
 - d. Total bilirubin $\leq 1.5 \times$ ULN (patients with known Gilbert's syndrome may have a total bilirubin up to $\leq 3 \times$ ULN).
 - e. Blood creatinine $\leq 1.5 \times$ ULN or calculated creatinine clearance ≥ 60 mL/min by the Cockcroft and Gault equation.

Note: A laboratory assessment may be repeated a maximum of two times during the Screening period to confirm eligibility.

9. Negative beta-human chorionic gonadotropin (β -HCG) pregnancy test within 7 days prior to start of study drug (C1D1) for women of childbearing potential.

10. Women of childbearing potential* must agree to use a highly effective** method of contraception from the time of giving informed consent until at least 16 weeks after the last dose of loncastuximab tesirine. Men with female partners who are of childbearing potential must agree that they will use a highly effective method of contraception from the time of giving informed consent until at least 16 weeks after the patient receives his last dose of loncastuximab tesirine.

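### The protocol gives two windows for skipping the pre-dose C1D1 pregnancy test, 7 days in Table 1 and 3 days in Section 8.3.6, and does not say which governs

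*Protocol*

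**What the plan says.** Four places in the protocol bear on the pregnancy test before the first dose.

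- **Section 5.1, inclusion criterion 9** (repeated in the synopsis) requires a negative "pregnancy test within 7 days prior to start of study drug (C1D1) for women of childbearing potential".
- **Table 1, Schedule of Events**, has a row "Pregnancy test, if applicable", which cites Section 8.3.6. The Day 1 cell for Cycles 1 and 2 carries footnote 5: "Not needed if screening assessment was performed within 7 days prior to C1D1".
- **Section 8.3.6** sets its own condition: the test before dosing on C1D1 "can be waived if the test for eligibility was done within 3 days of C1D1".
- **Section 4.2** fixes the interval in which a screening test can fall: "The screening period is from 28 days to 1 day prior to the start of the study drug".

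Section 8.3.6 also ties the eligibility test to "Inclusion criterion 10) and throughout the study as per SoE". In Section 5.1, criterion 10 is the contraception requirement, a highly effective "method of contraception from the time of giving informed consent until at least 16 weeks after the last dose of loncastuximab tesirine". The pregnancy test is criterion 9.

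The SAP mentions pregnancy tests only in Section 4.8.2, to say that the results go into the datasets and are not listed.

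**The concern.** Footnote 5 and Section 8.3.6 govern the same test, on the same day, in the same women, and they set different conditions for leaving it out. A coordinator working from the schedule and one working from the body text can therefore treat the same woman differently before her first dose. Monitors could also classify the same conduct differently, since a site that follows the footnote can be out of line with Section 8.3.6.

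This matters because of the drug. Section 1.2 describes a conjugate whose released toxin cross-links DNA, and pregnancy is an exclusion (Section 5.2, criterion 15). The pre-dose test is the last check before exposure. What is at stake is how recent that check is and whether sites apply it uniformly. No efficacy or safety analysis depends on it.

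**Working it through.** There is no statistical figure to reproduce. The check sets the windows side by side and counts days.

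**Inputs from the protocol**

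- Eligibility window: 7 days before C1D1 (Section 5.1, criterion 9).
- Waiver window in the schedule: 7 days (Table 1, footnote 5).
- Waiver window in the body text: 3 days (Section 8.3.6).
- Possible screening days: Day -28 to Day -1 (Section 4.2).

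**Comparison by day of the screening test**

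| Day of test | Footnote 5 | Section 8.3.6 | Agree? |
|---|---|---|---|
| -28 to -8 | C1D1 test needed | C1D1 test needed | Yes |
| -7 to -4 | Not needed | Not waived | **No** |
| -3 to -1 | Not needed | May be waived | Yes |

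**Size of the band.** Criterion 9 allows 7 pre-dose days (Day -7 to Day -1). Section 8.3.6 waives on 3 of them (Day -3 to Day -1). The conflict covers 7 - 3 = 4 days, and 4/7 = 57% of the window.

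**Age of the last negative test at first dose.** It is up to 7 days under footnote 5 and up to 3 days under Section 8.3.6, a difference of 7 - 3 = 4 days.

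**Does either text settle it?** Section 8.3.6 refers to the schedule for testing during the study, but its next paragraph states a specific 3-day condition, which would have no purpose if the footnote controlled. The Table 1 row in turn cites Section 8.3.6. The references are circular, and neither document has a precedence clause.

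**What each rule leaves of the C1D1 test.** Criterion 9 already requires a negative test within 7 days. Under footnote 5, every woman whose qualifying test came before C1D1 is therefore exempt, and the C1D1 test is needed only when it serves as the eligibility test itself. Under the 3-day rule the C1D1 test adds something beyond eligibility.

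**How many women might be affected (illustration only).** The documents give no count of women of childbearing potential. Assume they are 5% to 15% of the planned 140 patients: 140 × 0.05 = 7, and 140 × 0.15 = 21. If all have their eligibility test on Day -7 to Day -1, spread evenly, the band holds 7 × 4/7 = 4 to 21 × 4/7 = 12 women. With no assumption about the spread, the range is 0 to 21.

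**The case against.** The strongest reply is that nothing forces a site into non-compliance. Retesting on C1D1 satisfies both texts, and Section 8.3.6 is worded as a permission. The safeguards hold under either reading: a negative test within 7 days, pregnancy as an exclusion, highly effective contraception from consent, and on-study testing with drug held after a positive result. All of this stands, and it is why the point is minor. It does not remove the contradiction, because a site that relies on the footnote still omits a test that the body text does not waive.

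A second reply is that 7 days is the better supported window, since the synopsis, criterion 9 and footnote 5 all use it and only Section 8.3.6 says 3. The documents do not show which was intended, and a single 7-day window would also end the conflict. However, the synopsis and criterion 9 set the eligibility window, which is a separate matter from the waiver. A 7-day waiver would also leave the scheduled C1D1 test largely redundant with criterion 9. The 3-day rule satisfies both texts and is the more cautious one.

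Third, the reference to criterion 10 may not be a slip. Criterion 10 carries the asterisk that leads to the definition of childbearing potential, so the reference could be meant to show who is tested. That reading is possible. But the sentence concerns testing for eligibility, and that requirement is in criterion 9. Both criteria sit in the same section, so conduct is unlikely to be affected.

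Finally, the head-count rests on an unsourced share and an assumed spread of test days. That is correct, and the conclusion does not depend on it.

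**Conclusion.** The concern holds. The protocol sets two incompatible conditions for omitting the C1D1 pregnancy test and gives no rule for choosing between them. The conflict is confined to eligibility tests on Day -7 to Day -4. Its documented size is a 4-day difference in the maximum age of the last negative result at first dose. The estimate of 4 to 12 women (0 to 21 without the even spread) rests entirely on the assumptions stated with it.

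Severity is minor. The text is wrong as written, but the remaining safeguards keep the safety gap small. The primary endpoint, type I error, power, sample size and planned analyses are untouched. The wrong criterion number in Section 8.3.6 is a side point.

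**What to change.** 1. Reword Table 1 footnote 5 so that the C1D1 test is not needed only if the screening test was done within 3 days before C1D1, in line with Section 8.3.6.
2. Leave the 7-day eligibility window in criterion 9 as it is.
3. In Section 8.3.6, change the cross-reference from inclusion criterion 10 to inclusion criterion 9. If the pointer to the definition of childbearing potential is wanted, cite both.

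The cost is two short wording corrections, plus one repeat urine or blood β-HCG test for each woman whose eligibility test falls on Day -7 to Day -4. Section 8.3.6 already calls for that test.
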